## Appendix 2:Schedule of Activities: Schedule of Activities: Open-Label Extension Period (cont.)

- n Applicable only for RLD Visits 2 and 3.
- o Includes body temperature, pulse rate, and systolic and diastolic blood pressure while the patient is in a seated position. Vital signs are measured just before dosing and 15 (±5) minutes and 60 (±5) minutes after dosing for the first 5 OLE doses in case of study drug injection visit. Blood pressure and pulse measurements should be preceded by at least 5 minutes of rest for the participant in a quiet setting without distractions.
- p ECG should be performed prior to blood draws.
- q Hematology includes hemoglobin, hematocrit, RBC, WBC (absolute and differential: neutrophils, eosinophils, basophils, monocytes, lymphocytes, and other cells), quantitative platelet count.
- All clinical laboratory, PK, PD, ADA, and biomarker samples should be obtained pre-dose at indicated visits. Samples should be taken in the morning if possible, and approximately at the same time across visits.
- s If study drug was not administered on schedule because of a safety issue with laboratory abnormality, then the relevant laboratory parameter should be tested at the DD Visit.
- t Chemistry includes albumin, total protein, total bilirubin, ALP, AST, ALT, GGT, LDH, total cholesterol, LDL cholesterol, HDL cholesterol, triglycerides, ferritin, BUN, creatinine, sodium, Cl, K, Ca, P, complements (CH50, C3, C4), lipase, CRP, serum CK, and uric acid.
- u For patients on the corticosteroid taper with symptoms of AS early morning cortisol has to be measured. If morning cortisol is normal, but patient has symptoms of AS, perform low-dose ACTH stimulation test to confirm AS diagnosis.
- v Urine pregnancy tests will be performed at specified visits. If a urine pregnancy test is positive, the patient will not receive the scheduled dose, and a confirmatory serum pregnancy test will be performed. Urine β–hCG (sensitivity of at least 25 mU/mL) will be performed locally. *All female adolescent patients of childbearing potential who enter directly in the OLE will have a serum pregnancy test at screening.*
- W Samples for clinical laboratory tests should be collected pre-dose on dosing days. If any abnormalities are detected on urine dipstick tests (including urinary glucose, urinary protein, urinary occult blood, urobilinogen), a complete urinalysis (including microscopic of examination of urine) and/or urine culture is to be performed as deemed necessary.
- \* A TB test (e.g., tuberculin test and/or Quantiferon® test) should be conducted according to local guidance. If the patient is positive for latent TB, then the patient must be treated with appropriate anti-mycobacterial therapy for at least 4 weeks prior to initiating study treatment administration. Additional tests for the diagnosis of latent and active TB should be done as per the local guidance, including a chest X-ray or chest CT, in addition to the TB tests in individuals with a positive TB test or in individuals who have a potential risk for TB infection/TB reactivation (e.g., on immunosuppressive therapies, recently in contact with a person who has infectious TB disease, live in or recently traveled to a high-prevalence region/countries).
- For adolescent patients testing/sampling procedures will be adjusted in conformance with guidelines for pediatric blood volume limits from health authorities. Please refer to the laboratory manual for detailed instructions.
- z Quantitative immunoglobulins may include lgA, lgE, lgG and lgM.
- aa IgG subtypes include IgG1, IgG2, IgG3 and IgG4.

# Appendix 2:Schedule of Activities: Schedule of Activities: Open-Label Extension Period (cont.)

- bb HBsAg, HBcAb, HCVAb: All patients must have negative HBsAg test result at screening prior to enrollment. Hepatitis B screening: Patients who are HBsAg positive will be excluded from the study. If HBcAb status is positive, hepatitis B viral DNA will be measured. If HBV DNA is detectable, the individual must be excluded. If HBV DNA is undetectable, the individual may be enrolled. In these participants, HBV DNA measurement must be performed regularly at 12 weekly intervals during the study. Hepatitis C screening: If HCVAb is positive, HCV RNA will be measured. If HCV RNA is undetectable 3 12 weeks after HCV treatment completion, the patient can be enrolled.
- cc Hepatitis B viral DNA must be monitored every 12 weeks in patients whose HBcAb is positive and HBV DNA was negative at screening.
- dd Change in background therapy is allowed after Week 12 in the OLE period to ensure patients treated with placebo in the DB period have reached steady-state levels of satralizumab prior to steroid or IST taper.
- ee These assessments only apply to RLD Visits 1 and 3.
- ff PD measurements will include, but not be limited to IL-6 and sIL-6R.
-  RNA may be assessed for exploratory biomarkers including, but not limited to, plasmablast signature.
- hh For adolescent patients (at the time of informed consent) this sample is not to be collected.
- ii A single mandatory DNA sample will be collected for patient genotyping at the baseline visit. If the DNA sample is not collected at the baseline visit, it may be collected at any subsequent visit. Collection and submission of this sample is contingent upon the review and approval of the exploratory research by each site's IRB/EC and, if applicable, an appropriate regulatory body. If a site has not been granted approval for WGS sampling, collection of this sample will not be applicable at that site.
- ij Blood samples will be processed for flow cytometry (e.g., B-cell subsets).
- kk Autoantibodies will include AChR, MuSK and LRP4. Note that for sites in the Netherlands and Germany, the central laboratory autoantibody tests at screening to confirm gMG diagnosis are not required.
- Exploratory serum biomarkers may include but not be limited to autoantibodies (AChR, MuSK and LRP4) and IL-17.
- Plasma sample will also be collected at all visits following PBMC sample processing and will be stored for biomarker research.
- m Sample types to be collected for research purposes if a patient signs the Optional RBR Informed Consent Form.

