#### STUDY TREATMENT

Weight-tiered dosing via SC injection will be used in this study.

Table 3 Dosing Regimen: Double-Blind Period

Body Weight at Baseline a	Dose and Regimen
≤100 kg	120 mg satralizumab/placebo administered at Weeks 0, 2, 4 (loading doses), and maintenance doses Q4W thereafter as a SC injection
>100 kg	180 mg satralizumab/placebo administered at Weeks 0, 2, 4 (loading doses), and maintenance doses Q4W thereafter as a SC injection

SC= subcutaneous, Q4W= every 4 weeks.

During the OLE period, all patients will receive open-label treatment with 120 mg or 180 mg satralizumab, as determined based on body weight (see above). *Adult and adolescent* patients who receive placebo during the DB period will receive satralizumab SC loading doses at Weeks 0, 2, and 4 in the OLE, followed by maintenance doses every 4 weeks (Q4W) thereafter during the OLE period. *Adult and adolescent* patients who receive active treatment during the DB period will continue receiving satralizumab SC Q4W during the OLE period, but will receive an additional placebo SC injection at Week 2 to maintain blinding to DB treatment assignment.

Adolescent patients who first enter the study in the OLE period will receive satralizumab SC loading doses at Week 0, 2, and 4 in the OLE, followed by maintenance doses Q4W thereafter and will remain on stable background therapy until Week 24 of the OLE.

Information on delayed or missed doses, as well as background therapy and rescue medication, can be found in the protocol.

Only adult patients aged  $\geq$  18 years old will be included at participating sites in France

Recommendations in case of changes in body weight in an individual patient would result in a different dosing band are given in the protocol.

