#### 3.1.3 Adolescent Patients

As of global protocol Version 5, all adolescent patients enrolled into the study will directly enter the OLE period after completion of screening (see Figure 1).

Adolescent patients enrolled directly into the OLE will remain on stable background therapy until Week 24 of the OLE (Section 3.4.8).

Adolescent patients enrolled through previous versions of the protocol (prior to global protocol Version 5) will continue in the study as follows:

• Adolescent patients randomized in the DB period prior to the randomization of the last adult patient in the DB period will continue on randomized, DB study drug for 24 weeks and can then enter the OLE period (after completion of the DB period) to start open-label satralizumab, remaining on stable background therapy until Week 12 OLE

• Adolescent patients randomized in the DB period after the randomization of the last adult patient in the DB period will enter the OLE period (without completion of DB period) to start open-label satralizumab, remaining on stable background therapy until Week 12 OLE

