### 3.1.4 Open-Label Extension Period

Patients who complete the DB period can enter the OLE period. As of global protocol Version 5, adolescent patients will directly enter the OLE period after completion of screening (see Section 3.1.3). Patients who experience a clinical exacerbation that requires rescue therapy during the DB period may continue in the study until the end of the DB period and can enter the OLE period upon completion of treatment and assessments in the DB period.

For adult and adolescent patients who complete the DB period, the final visit of the DB period coincides with the Week 0 visit of the OLE period and is, therefore, considered the OLE baseline. The assessments performed at Week 24 of the DB period will be used as the active treatment baseline for the patients who receive placebo during the DB period and as the OLE baseline for patients who receive satralizumab during the DB period. Upon completion of the Week 24 assessments all patients will receive open-label treatment with satralizumab.

In the OLE period, all patients will receive open-label treatment with 120 mg or 180 mg satralizumab, as determined based on body weight. Patients who receive placebo during the DB period will receive satralizumab SC loading doses at Weeks 0, 2, and 4 in the OLE, followed by maintenance doses Q4W thereafter during the OLE period. Patients who receive active treatment during the DB period will continue receiving SC satralizumab Q4W during the OLE period but will receive an additional placebo SC injection at Week 2 to maintain blinding to DB treatment assignment.

For adult and adolescent patients who first enter the study randomized in the DB period, to ensure a period of satralizumab treatment stability in patients previously treated with placebo, dose reduction (taper) of background therapy (OCS, IST, and/or AChEls) can be started at or after Week 12 of the OLE period at the discretion of the investigator.

Adolescent patients who first enter the study in the OLE period will receive satralizumab SC loading doses at Weeks 0, 2, and 4 in the OLE, followed by maintenance doses Q4W thereafter.

Further details on adolescent patients in the OLE period are provided in Sections 3.1.3 and 3.4.8.

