#### 3.4.8 Rationale for Open-Label Extension

Following the 24-week DB period, the study will include an OLE period of approximately 2 years from last patient in the global study. *Adolescent patients will be enrolled directly in the OLE after completion of screening (see Section 3.1.3)*. The objectives of the OLE are to evaluate satralizumab long-term safety and efficacy, including steroid/IST sparing, in patients with gMG.

The adolescent OLE aims to evaluate pharmacokinetics, pharmacodynamics, safety, and efficacy of satralizumab in adolescents aged  $\geq 12$  years to  $\leq 18$  years old with gMG.

This study will enroll patients on stable background therapy, including OCSs and ISTs as indicated in Section 3.1.

Long-term steroid treatment is associated with numerous adverse effects on many organ systems, including bone (osteoporosis, avascular necrosis), muscle (myopathy), metabolism and endocrine organs (weight gain, impaired glucose tolerance, hypothalamic-pituitary-adrenal suppression), skin (skin atrophy, acne, striae), eyes (glaucoma, cataract), behavior and mood (mood disorders, insomnia), cardiovascular system (hypertension, fluid retention, perturbations of serum lipoproteins), GI system (gastritis, peptic ulcer disease), and immune system (increased risk of infection). One of the key treatment goals in MG is to reduce exposure to steroids (Sanders et al. 2016; Jaretzki et al. 2000). The adverse event profile of the steroid-sparing ISTs that constitute the background therapy in this study includes renal toxicity with the use of cyclosporine, myelosuppression, infections, liver toxicity, and malignancies (Vodopivec et al. 2014; Collins et al. 2019)

At or after Week 12 of the OLE, tapering of steroids and IST background treatment will be allowed based on clinical judgement *for adult and adolescent patients randomized in the DB period at study start.* Satralizumab dosing until Week 12 of the OLE is required to ensure that patients treated with placebo during the DB period have reached steady-state satralizumab concentrations.

Adolescent patients enrolled directly in the OLE will remain on stable background therapy until Week 24 of the OLE period.

The ability of patients to successfully taper steroids or ISTs while concurrently taking satralizumab will be evaluated in the OLE period based on analyses that will be prespecified in the statistical analysis plan (SAP).

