# 4.3.2.3 Background Therapy

In the DB period (in addition to satralizumab or placebo) patients will receive background treatment with OCSs and/or IST and/or AChEls at a stable dose not exceeding the following doses:

- Azathioprine: 3 mg/kg/day for adults, 2.5 mg/kg/day for adolescents (O'Connell et al. 2020)
- Mycophenolate mofetil: 3000 mg/day for adults, 2000 mg/day for adolescents
- Cyclosporin A: 5 mg/kg/day
- Tacrolimus: 0.2 mg/kg/day for adults, 0.1 mg/kg/day for adolescents (Ponseti et al. 2008)
- Oral glucocorticoids: 30 mg/day (prednisone equivalent)
- Pyridostigmine: 600 mg/day for adults, up to 1.5 mg/kg 5 times per day for adolescents (maximum 450 mg/day) (O'Connell et al. 2020)
- Neostigmine: 375 mg/dayAmbenonium: 300 mg/day

These are considered *AxMPs* (for use in the EEA), see Appendix 15.

In addition to OCSs, only one IST or immunomodulatory drug at a stable dose is allowed during the DB period (see Section 4.1.1).

AChEls **should not be taken for 10 hours prior** to completion of efficacy assessments including QMG and MGC testing at each study visit (except screening visit) if medically safe to do so.

In the DB period and the first 12 weeks of the OLE period a dose decrease of baseline treatments is permitted only for safety reasons. Dose increase or change of background treatment is strongly discouraged.

In the OLE period, background treatment, for all *adult and adolescent* patients *randomized in the DB period at the start of the study*, should be maintained stable for at least the first 12 weeks to allow satralizumab levels to reach steady state in the patients who received placebo during the DB period. Patients can be tapered off steroids, ISTs, and AChEls after Week 12 of the OLE period based on the investigator's judgment.

For adolescent patients enrolled directly into the OLE, stable background therapy should be maintained until Week 24 of the OLE period (see Section 3.1.3).

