#### 4.5 STUDY ASSESSMENTS

The schedule of activities to be performed during the study is provided in Appendix 1 (DB period) and Appendix 2 (OLE period). All activities should be performed and documented for each patient.

Patients will be closely monitored for safety and tolerability throughout the study. Patients should be assessed for toxicity prior to each dose; dosing will occur only if the clinical assessment and local laboratory test values are acceptable.

At applicable sites, certain study assessments, including study drug administration, may be performed by a mobile nurse (MN) professional at the patient's home or another suitable location, to improve access and convenience for patients participating in the study. The Sponsor will select a healthcare company that will be responsible for providing MN services for participating sites (the MN vendor). The MN vendor is responsible for ensuring that all MN professionals are licensed, qualified, and in good standing, as per applicable regulations, and that appropriate background checks have been performed. If the investigator at a participating site determines that MN services are appropriate for a patient and the patient gives written informed consent to participate

in MN visits, the MN network will communicate with the patient and the patient's site. MN visits will be scheduled on specified visit days, to allow for relevant assessments to be performed by the MN professional. The schedule of activities (see Appendix 1 and Appendix 2) will specify the assessments that may be performed by an MN professional.

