Appendix 2:Schedule of Activities: Schedule of Activities: Open-Label Extension Period (cont.)

	Screening a			From	Week	0 to W	eek 24	1			After V	Veek 24		US Visit	DD Visit b	RLD Visit 1,2,3 c	EOT Visit d	SFU/ EOS Visit e
Week	−4 to −1	O f, g	2	4	8	12	16	20	24	Q4W h	Q12W	Q24W	Q48W					
Window in days	NA	NA	±3	±3	±7	±7	±7	±7	±7	±7	±7	±7	±7				±7	±7
lgG subclasses	x	x				x			х				х			х¹	x	х
Hepatitis Test bb	x																	
Hepatitis B viral DNA cc	x	x				x			х		х	х	х	X		х	X	x
Concomitant medications	x	x	х	х	x	x	x	x	х	х	х	x	х	X	х	х	X	x
Adverse events	х	Х	Х	Х	Х	Х	Х	Х	Х	x	Х	х	х	Х	Х	Х	x	Х
Record if any changes in background therapy dd				х	х	х	х	х	x		х	х	х		x		х	x
Efficacy																		
MG-ADL	x	X	Х	X	X	Х	X	X	Х			X	X	X		X	X	
QMG	x	X	Х	X	Х	Х	Х	X	Х			X	X	X		X	X	
MGC	x	Х	Х	X	X	Х	X	X	X			X	X	X		X	X	
MG-QOL 15r (revised)	x	x	х	x	x	x	x	x	х			x	Х	Х		Х	x	
NeuroQoL Fatigue Subscale	x	х	х	x	x	х	x	х	х			х	х			X ee	x	
EuroQoL EQ- 5D-5L		х										х	х			х¹	х	

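### Appendix 2 footnote dd and one sentence in Protocol 4.3.2.3 set a Week 12 limit on background-therapy changes for every OLE patient, although adolescents enrolled directly into the OLE must stay stable to OLE Week 24

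*Protocol*

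**What the plan says.** The Protocol has two stability periods in the OLE. Patients randomized in the DB period may begin to taper at or after OLE Week 12; Section 3.1.4 opens that rule with its cohort: "For adult and adolescent patients who first enter the study randomized in the DB period, to ensure a period of satralizumab treatment stability". Adolescents enrolled directly into the OLE, a route added in Version 5, have a longer period, stated in four places:

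- Synopsis, Study Treatment: "maintenance doses Q4W thereafter and will remain on stable background therapy until Week 24 of the OLE"
- Section 3.1.3: "Adolescent patients enrolled directly into the OLE will remain on stable background therapy until Week 24 of the OLE"
- Rationale, Section 3.4.8: "Adolescent patients enrolled directly in the OLE will remain on stable background therapy until Week 24 of the OLE period"
- Section 4.3.2.3: "For adolescent patients enrolled directly into the OLE, stable background therapy should be maintained until Week 24 of the OLE period"

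Two places give Week 12 without saying whom it covers.

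- Appendix 2, footnote dd, reads: "Change in background therapy is allowed after Week 12 in the OLE period to ensure patients treated with placebo in the DB period have reached". The rest of the sentence names steady-state satralizumab levels before any steroid or IST taper. The footnote is attached to the row "Record if any changes in background therapy", which all OLE patients share.
- Section 4.3.2.3, in a separate sentence, permits decreases of baseline treatment only for safety reasons during the DB period and the first 12 weeks of the OLE.

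**The concern.** Appendix 2 applies to adolescents enrolled directly into the OLE. Section 4.5 makes it the OLE schedule and wants its activities done for each patient. Section 4.5.2 sends these adolescents to it for screening. A site working from the schedule would see a permission to change background therapy after Week 12 and nothing to say that this cohort must wait until Week 24. A site that then turned to the dose-decrease sentence in 4.3.2.3 would find the same Week 12 boundary.

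The longer period protects the interpretation of an uncontrolled cohort. If OCS, IST or AChEI doses change between Weeks 12 and 24, the later scores reflect both satralizumab and the background change, and no concurrent comparison can separate them.

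**Working it through.** The plan states no figure to reproduce. The check compares the texts and then counts the visits in the gap.

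**Step 1: the rules side by side, for an adolescent enrolled directly into the OLE**

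| Source | Rule as written | Cohort named? |
|---|---|---|
| Synopsis; 3.1.3; 3.4.8; 4.3.2.3 (last paragraph) | Stable until OLE Week 24 | Yes, direct-OLE adolescents |
| 3.1.4; 3.4.8; 4.5.8.2 (MGC) | Week 12 rule | Yes, patients randomized in the DB period |
| 4.3.2.3, taper sentence | Taper after OLE Week 12 | Not in the sentence; the one before it names DB-randomized patients |
| 3.1.1 | Stable until OLE Week 12 | No, but it stands under the Double-Blind Period heading |
| 4.3.2.3, dose-decrease sentence | Safety reasons only, through the first 12 weeks of the OLE | No |
| Appendix 2, footnote dd | Change allowed after OLE Week 12 | No |

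The first row is the intended rule. The second is consistent with it, and in the third and fourth the adjacent text supplies the scope. The last two have no such limit. Footnote dd conflicts directly, because it grants a permission. The dose-decrease sentence conflicts by implication, because its restriction ends 12 weeks too early for this cohort.

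**Step 2: does Appendix 2 name cohorts when it means to?** Yes. Footnote a is confined to adolescents who first enter in the OLE, f to patients who complete the DB period, g to adolescents who move over without completing it, and v has a sentence for female adolescents who enter directly. Footnote dd has no such wording.

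**Step 3: size of the gap**

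- Weeks: 24 − 12 = 12 of the 24 weeks of required stability.
- Post-baseline MG-ADL visits to OLE Week 24 in Appendix 2: Weeks 2, 4, 8, 12, 16, 20 and 24, so 7.
- Visits after Week 12: Weeks 16, 20 and 24, so 3 of 7 (3/7 = 43%).
- QMG, MGC, MG-QOL 15r and Neuro-QoL Fatigue are scheduled at the same visits. EQ-5D-5L is not scheduled between Weeks 2 and 24.

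**Step 4: reach into the analyses.** The SAP (1.2) states that adolescents enrolled directly into the OLE are not part of the primary analysis. Section 6 of the Protocol requires a post-baseline MG-ADL assessment in the DB period for the mITT population, which they cannot have. Adolescent efficacy is summarized descriptively (Protocol 6.4.8; SAP 4.6.4.1).

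**The case against.** The best defence is that footnote dd, read whole, limits itself. Its stated purpose concerns patients who had placebo in the DB period, and direct-OLE adolescents had no DB period. The same reason appears in 3.1.4, 3.4.8 and 4.3.2.3 in connection with DB-randomized patients. This is good evidence of intent, but the clause explains the timing and does not say who may change therapy. These adolescents also receive the same loading doses at Weeks 0, 2 and 4 as former placebo patients, so a reader could think the steady-state reason fits them too.

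A second defence is that the specific rule prevails. It is stated four times, once in the section that governs background therapy. A permission to taper is not a scheduled activity, so Section 4.5 gives the footnote no priority over 4.3.2.3. This stands, and it is the main reason the point is minor: harm requires a site to rely on general wording and overlook four specific statements. Nothing in the documents shows that this has happened.

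A third is even-handedness: if context may supply the scope of 3.1.1 and of the taper sentence in 4.3.2.3, it should do so for dd. But those two have a heading or a preceding sentence that names the group. Footnote dd hangs on a row shared by all OLE patients.

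**Conclusion.** The point holds as a minor inconsistency. Two pieces of text are wrong as written for adolescents enrolled directly into the OLE, by 12 weeks and three efficacy visits. All three visits are affected only if a site acts on the Week 12 wording and changes therapy before the Week 16 visit; a later change affects fewer. The documents give neither the size of this cohort nor a rate of early changes, so no shift in means or responder rates can be estimated. Changes in background therapy are recorded from OLE Week 4, so an early one would be visible afterwards, though not prevented.

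Three stronger readings are tempting and are not supported:

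- A reader might infer that footnote dd is the only slip and that the body text always confines the Week 12 rule to DB-randomized patients. The dose-decrease sentence in 4.3.2.3 does not, and 3.1.1 does so only through its heading.
- A reader might multiply the three visits by the five scores and report 15 of 35 assessments as exposed. That counts the same three visits five times.
- A reader might infer a threat to the main efficacy results. These adolescents are outside the mITT population and their data are descriptive, so the primary analysis, alpha and power are unaffected.

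**What to change.** Make two wording changes at the next amendment.

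1. Reword footnote dd along these lines: *Background therapy may be changed after OLE Week 12 in patients randomized in the DB period, and after OLE Week 24 in adolescents enrolled directly into the OLE.*
2. In 4.3.2.3, extend the safety-only restriction on dose decreases to OLE Week 24 for adolescents enrolled directly into the OLE. This also gives a safety-driven decrease between Weeks 12 and 24 an explicit basis for this cohort, which the current sentence does not.

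The cost is two sentences, with no new data collection. No SAP change is required: the tapering summaries in SAP 4.4.3 count reductions after OLE Week 12, and a reduction after Week 24 meets that definition.
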